7.4 Sensitivity Analyses

A sensitivity of the primary analysis using multiple imputation for missing data will be performed for the primary endpoint to assess the impact of missing data after subject's have dropped out. For the primary endpoint the following two sensitivity analyses will be conducted:

7.4.1 Missing as Missing

The primary endpoint analysis will be conducted without any imputation.

7.4.2 Multiple Imputation

All missing data for these subjects will be imputed using multiple imputation procedures. However, the multiple imputation is used for subjects that have some baseline and postbaseline data, i.e., if a subject is missing all pre and post baseline data, no data will be imputed.

The imputation will be carried out in SAS version 9.4 or later, using the full conditional specification method (FCS) with a regression model approach (Carpenter and Kenward, 2013). The variables included sequentially in the model are:

- Treatment as a main effect
- Site and baseline pain intensity as covariates
- SPID for each time point as the dependent variable

The analysis model will be an analysis of covariance (ANCOVA) with NRS-SP1D 48 as the dependent variable, treatment as a main effect and site and baseline pain intensity as the covariates.

The ANCOVA results from the multiply imputed datasets will be combined using the usual Rubin's rules for multiple imputation (Little and Rubin, 1987) and will be done in SAS using PROC MIANALYZE. A significance test of the treatment difference at the two-sided 0.05 level and corresponding 95% confidence intervals will be calculated.

7.5 Multiple Clinical Trials

This is a multi-center clinical trial with two sites.

7.6 Multiple Comparisons and Type I Error Rate Multiplicity adjustments

There will also be no Type I error adjustment on the hypotheses testing of this Phase 2 study.

7.7 Covariates and Prognostic Factors

Baseline pain intensity and site would be used as covariates for the analysis of the primary efficacy endpoint. Other prognostic factors may be included in the analysis model if they are found to be contributing factors.

7.8 Subgroups and Exploratory Analysis

There is no planned subgroup analysis; however subgroup and exploratory analysis may be conducted as postHoc analysis.

7.9 Standard Calculations

7.9.1 Age

Age will be calculated as the number of completed years between the date of informed consent and the subject's birth date.

Age (years) = integer of [(date of informed consent – date of birth)/ 365.25 + 0.5]

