3.2. Subject Selection

3.2.1. Inclusion Criteria

All subjects must satisfy the following criteria to be considered for study participation:

1. Is able to speak and understand the language in which the study is being conducted, is able to understand the procedures and study requirements, and has voluntarily signed and dated an informed consent form approved by an IRB before the conduct of any study procedures;
2. Is a male or female ≥ 18 and ≤ 65 years of age;
3. Is classified using the American Society of Anesthesiologists Physical Status Classification System as P1 to P2;
4. Has undergone primary, unilateral, distal first metatarsal bunionectomy (osteotomy and internal fixation) with no additional collateral procedures;
5. Experiences a pain intensity rating of ≥ 4 on an 11-point (0-10) Numeric Rating Scale (NRS) during the 9-hour period after discontinuation of the anesthetic block;
6. Has a body weight ≥ 45 kg and a body mass index (BMI) ≤ 40 kg/m²;
7. If female and of childbearing potential, is non-lactating and non-pregnant (has negative pregnancy test results at Screening [serum] and on Day 0 before surgery [urine]);
8. If female, is either not of childbearing potential (defined as postmenopausal for at least 1 year or surgically sterile [bilateral tubal ligation, bilateral oophorectomy, or hysterectomy]) or practicing 1 of the following medically acceptable methods of birth control:
 - a. Hormonal methods such as oral, implantable, injectable, vaginal ring, or transdermal contraceptives for a minimum of 1 full cycle (based on the subject's usual menstrual cycle period) before study drug administration
 - b. Total abstinence from sexual intercourse since the last menses before study drug administration
 - c. Intrauterine device
 - d. Double-barrier method (condoms, sponge, or diaphragm with spermicidal jellies or cream)

9. Is willing and able to comply with study requirements (including diet, alcohol, and smoking restrictions), complete the pain evaluations, remain at the study site for ≥ 72 hours, and return for a follow up visit 7 ± 2 days after surgery.

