4. SAMPLE SIZE DETERMINATION AND RATIONALE, STATISTICAL POWER, AND SIGNIFICANCE LEVEL

A total of 45 subjects are planned to be enrolled for the study. A sample size of 15 subjects per treatment group will provide $\geq 80\%$ power to detect a minimal standardized effect size of 0.5 between the 100 μg q4h, 200 μg q4h active treatment arms, and placebo in NRS SPID-48 using a 3-group analysis of covariance (ANCOVA) with baseline NRS score as the covariate with a 0.05 two-sided significance level (EAST v6).

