8.1.3 Demographics and Baseline Characteristics

Demographic and baseline characteristics (including age, gender, race, weight, height, BMI, surgery duration, and baseline pain intensity) will be summarized by treatment group and for the overall population by descriptive statistics. No formal statistical analyses will be performed. Medical history, clinical laboratory test results, and urine drug screen, alcohol breathalyzer test, X-ray and podiatric examination assessments will be listed.

The analyses of demographics and baseline characteristics will be conducted for the safety population.

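### SAP 7.9.1 defines age as completed years, but its formula rounds to the nearest year, so about half of subjects would be tabulated one year above their completed age

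*SAP*

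**What the plan says.** SAP 7.9.1 gives two rules for one variable. In words: "Age will be calculated as the number of completed years between the date of informed consent" and the birth date. As a formula: the integer of the consent date minus "date of birth)/ 365.25 + 0.5", with the 0.5 inside the bracket whose integer is taken. No other section of either document gives a different derivation of age or reconciles the two.

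Age is used as follows:

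- Protocol 3.2.1, criterion 2: "Is a male or female ≥ 18 and ≤ 65 years of age".
- SAP 8.1.3: "Demographic and baseline characteristics (including age, gender, race, weight, height, BMI, surgery duration, and baseline pain intensity) will be summarized by treatment group" and overall, descriptively and without formal analysis. SAP 8.1 includes the minimum and maximum among the summary statistics.
- SAP 7.7: "Baseline pain intensity and site would be used as covariates for the analysis of the primary efficacy endpoint". Age is not named there, although the section adds: "Other prognostic factors may be included in the analysis model if they are found to be contributing factors".

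**The concern.** Adding one half and then taking the integer part is the usual way to round to the nearest whole number. It does not count completed years. A programmer who follows the sentence and one who follows the formula would get different ages for roughly half the subjects. Independent programming would then either fail to match or repeat the same error.

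What is at stake is the accuracy of the age row in the demographic table and its agreement with the protocol's age limits. A maximum of 66 in a trial capped at 65 would prompt an eligibility query with nothing behind it.

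**Working it through.** The plan states no figure that depends on this rule, so there is nothing to reproduce. The check compares the two rules directly.

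**Inputs**
- Definition and formula: SAP 7.9.1.
- Age limits 18 to 65: Protocol 3.2.1, read as completed years. The criterion does not say this itself.
- Number of subjects: SAP 4, "A total of 45 subjects are planned to be enrolled for the study".
- Assumptions not in the documents: birthdays spread evenly over the year, ages uniform over 18 to 65, and consent dates starting on 1 October 2016.

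**Formulas**, with d = days from birth to consent
- SAP formula: int(d/365.25 + 0.5)
- Without the 0.5: int(d/365.25)
- Completed years: consent year − birth year, minus 1 if the birthday has not been reached in the consent year

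**Single cases**

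| Born | Consent | d | d/365.25 | Completed | SAP formula | Without 0.5 |
|---|---|---|---|---|---|---|
| 15 Jan 1976 | 1 Oct 2016 | 14,870 | 40.712 | 40 | 41 | 40 |
| 15 Jun 1976 | 1 Oct 2016 | 14,718 | 40.296 | 40 | 40 | 40 |
| 15 Jan 1951 | 1 Oct 2016 | 24,001 | 65.711 | 65 | 66 | 65 |
| 15 Jan 1998 | 15 Jan 2016 | 6,574 | 17.9986 | 18 | 18 | 17 |

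The third row is an eligible subject tabulated above the protocol limit. The fourth shows why deleting the 0.5 is not quite enough: 365.25 is an average year length, so the quotient can fall just short of a whole number on the birthday itself.

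**All cases.** Thirty consent dates were crossed with every birth date giving a completed age of 18 to 65, which makes 525,960 pairs.
- SAP formula: 50.1% agree with completed years, 49.9% are exactly one year high, none is low.
- Without the 0.5: 99.97% agree, 0.03% are one year low.
- Eligible subjects given an age of 66 by the SAP formula: 1.04%. By hand: half of one of 48 age years, 0.5/48 = 1.04%.

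**Applied to 45 subjects**
- Expected number overstated: 45 × 0.499 = 22.5. The binomial probability of 16 to 29 is 96%.
- Shift in the mean relative to completed years: 0.499 × 1 ≈ 0.5 year.
- Expected number of eligible subjects shown as 66: 45 × 0.0104 ≈ 0.47.

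**The other reading of the formula.** If integer-of meant rounding instead of truncation, the result would be worse. Any fraction of a year above zero, plus 0.5, would then round up, and nearly every age would be one year high.

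**The case against.** The strongest reply is that very little depends on this. Age is purely descriptive in the plan: it is not a named covariate, SAP 2.4.2 stratifies by center only, and SAP 7.8 plans no subgroup analysis. The expected shift is the same in every arm. All of this stands.

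A reader might go further than the documents allow in three ways.

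- **That the formula could admit or hide an under-age subject.** It does map 17.6 to 18. But eligibility is judged against the inclusion criteria at Screening (Protocol 7.1) and again before surgery (Protocol 7.2.1), not from the derived variable. Age is itself a demographic item collected at Screening (Protocol 6.2.1), and SAP 8 lists all collected data. SAP 8.1.2 has deviations classified before unblinding, and SAP 10.1 plans eligibility and deviation listings.
- **That the reported mean age would be wrong in an absolute sense.** Under evenly spread birthdays, nearest-year rounding is on average unbiased for exact decimal age, while completed years lie about 0.5 year below it. The 0.5-year excess is a departure from the SAP's stated definition, not an error about how old subjects are.
- **That efficacy results would be distorted if age entered the model through the open clause in SAP 7.7.** Apart from their different average offsets, which the intercept absorbs, both versions scatter around exact age by the same amount: a uniform error one year wide, with SD 1/√12 ≈ 0.29 year. Neither is a worse covariate in any way that matters.

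The contradiction could also be removed by changing the sentence to say nearest year. That would be consistent, but it would leave eligible 65-year-olds appearing as 66.

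**Conclusion.** The definition and the formula in SAP 7.9.1 contradict each other, and neither way of taking the integer reconciles them. That conclusion needs no assumption.

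The size does. With birthdays spread evenly over the year, about half of subjects are reported one year above their completed age, and the mean is raised by about 0.5 year relative to the mean of completed years. The 1% figure for eligible subjects shown as 66 also assumes uniform ages and that the upper limit of 65 means completed years. Fewer subjects near the limit would make it smaller.

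The effect is confined to the demographic table and the listings of derived age. Eligibility decisions, SPID-48, power and alpha are untouched. This is a minor correction, worth making because it is certain and nearly free.

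**What to change.** In SAP 7.9.1 keep the sentence and replace the formula with a calendar-anniversary rule: age equals the consent year minus the birth year, minus 1 if the consent month and day fall before the birth month and day. This removes the 0.5 and also the rare birthday error that comes from dividing by 365.25.

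The cost is one line of the SAP and one derivation in the programs, best changed before the tables are programmed. Design, conduct and data collection do not change.

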7.9.2 Height

For summary purposes height will be expressed in centimeters. Entries made in inches will be converted to centimeters using the formula noted below.

Height (cm) = Height (in)*2.54

7.9.3 Weight

For summary purposes weight will be expressed in kilograms. Entries made in pounds will be converted to kilograms using the formula noted below.

Weight (kg) = Weight (lb)/ 2.2046

7.9.4 Body Mass Index (BMI)

BMI will be calculated using height (in cm) and weight (in kg) according to the formula noted below.

BMI (kg/m²) = weight (kg) / [height (cm)/100]²

7.9.5 Pain Intensity (PI)

Subjects will assess their current pain intensity using an 11-point (0 to 10) Numerical Rating Scale (NRS). Each subject will be instructed to mark the number indicating his or her current pain intensity.

The subject is to record pain intensity (NRS) in the inpatient subject diary at Baseline before the first dose of study drug (Day 1), at Time 0. Thereafter, the subject is to record NRS pain intensity assessments at the following time points during the 48-hour period after Time 0:

- 2.5, 5, 15, 30, and 45 minutes and 1, 1.5, 2, 3, 4, 5, 6, 7, 8, 12, 16, 20, 24, 32, 40 and 48 hours after Time 0, and immediately before each use of rescue analgesia.

i	Nominal Ti (hours)
0	0
1	0.0417

i	Nominal Ti (hours)
2	0.0833
3	0.25
4	0.5
5	0.75
6	1
7	1.5
8	2
9	3
10	4
11	5
12	6
13	7
14	8
15	12
16	16
17	20
18	24
19	32
20	40
21	48

7.9.6 Pain Intensity Difference (PID)

Pain intensity difference (PID) is to be calculated by subtracting the pain intensity at each time point from the pain intensity at time 0.

$$PID_i = PI_i - PI_0$$

7.9.7 Summed Pain Intensity Difference (SPID)

The summed pain intensity difference (SPID) is to be calculated by multiplying the PID score at each post dose time point by the duration (in hours) since the preceding time point and then summing the values over the relevant time period.

$$SPID-48 = \sum_{i=1}^{21} (T_i - T_{(i-1)}) * PID_i$$

$$SPID-24 = \sum_{i=1}^{18} (T_i - T_{(i-1)}) * PID_i$$

$$SPID-8 = \sum_{i=1}^{14} (T_i - T_{(i-1)}) * PID_i$$

$$SPID-4 = \sum_{i=1}^{10} (T_i - T_{(i-1)}) * PID_i$$

Where $T_0 = 0$, T_i is the actual time, and PID_i is the PID score at time T_i .

The durations between nominal time points will be calculated using the actual times of the pain score measurement. If the actual time is missing the nominal planned time will be used.

7.9.8 Pain Relief (PAR)

Subjects will assess their current pain relief using a 5-point categorical scale. Each subject will be instructed to mark the number indicating his or her current pain relief.

The subject is to record pain relief (5-point categorical rating scale) in the inpatient subject diary at the following time points during the 48-hour period after Time 0:

- 2.5, 5, 15, 30, and 45 minutes and 1, 1.5, 2, 3, 4, 5, 6, 7, 8, 12, 16, 20, 24, 32, 40 and 48 hours after Time 0, and immediately before each use of rescue analgesia.

7.9.9 Total Pain Relief (TOTPAR)

Total pain relief (TOTPAR) is calculated by multiplying the pain relief score at each time point by the duration (in hours) since the preceding time point and then summing these over the relevant time period.

$$TOTPAR-T_k = \sum_{i=1}^k (T_i - T_{(i-1)}) * PAR_i$$

$$TOTPAR-48 = \sum_{i=1}^{21} (T_i - T_{(i-1)}) * PAR_i$$

$$TOTPAR-24 = \sum_{i=1}^{18} (T_i - T_{(i-1)}) * PAR_i$$

$$TOTPAR-8 = \sum_{i=1}^{14} (T_i - T_{(i-1)}) * PAR_i$$

$$TOTPAR-4 = \sum_{i=1}^{10} (T_i - T_{(i-1)}) * PAR_i$$

7.9.10 Two-Stopwatch Assessment of Pain Relief

Time to perceptible pain relief and meaningful pain relief will be evaluated using the 2 stopwatch method (after the first dose only). The study staff will start 2 stopwatches as soon as the first dose of study drug is administered. Each subject will be instructed to stop the first stopwatch when he or she experiences any perceptible pain relief and the second stopwatch when he or she experiences pain relief that is meaningful to them. Subjects will receive training for this procedure at their screening visit and prior to discontinuation of the regional anesthetic popliteal block.

7.9.11 Time to onset of analgesia

Time to onset of analgesia is the time that the first stopwatch is stopped (when the subject experiences first perceptible pain relief) given that the second stopwatch is stopped (when the subject experiences meaningful pain relief). If both stopwatches are not stopped or just one stopwatch is stopped, then the time to analgesia will be censored at the time of the second dose or the use of rescue medication, whichever comes first.

7.9.12 Peak Pain Relief

Peak pain relief is the highest value of pain relief experienced during the study. Values of pain relief after use of rescue medication for pain (up to four hours after use) will be replaced by the pain relief score collected prior to that use of rescue medication.

7.9.13 Time to Peak Pain Relief

Time to peak pain relief is the first time when the highest value of pain relief is observed. If no pain relief is observed then the time will be censored at the time of the last assessment.

7.9.14 Time to first Perceptible Relief

Time to first perceptible relief is the time when the subject experiences any perceptible pain relief after administration of study drug and stops the first stopwatch (irrespective of the second stopwatch). If it is not stopped, time will be censored at the time that the second stopwatch is stopped, the time of the second dose, or the first time that rescue medication was used, whichever comes first.

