7.3.2. Post-randomization

1. Measure vital signs (resting blood pressure, heart rate, respiratory rate, and oral body temperature) immediately before and 1 hour after the first dose of study drug on Day 0, then immediately before and 1 hour after the 24-hour and 40-hour doses, and at 48 hours.
2. Perform a 12-lead ECG before the first dose of study drug, and then at 90 minutes and 12, 24, and 48 hours after Time 0.
3. Pulse oximetry will be recorded at selected times, including baseline before Time 0 and at 90 minutes and 12, 24, and 48 hours after Time 0 (Tmax).
4. The subject is to record pain intensity (numerical rating scale) in the inpatient subject diary at Baseline before the first dose of study drug (Day 1). Thereafter, the subject is to record pain intensity and pain relief (5-point categorical scale) assessments at the following time points:
 - a. At 2.5, 5, 15, 30, and 45 minutes and 1, 1.5, 2, 3, 4, 5, 6, 7, 8, 12, 16, 20, 24, 32, 40 and 48 hours after Time 0, and immediately before each use of rescue analgesia.
 - b. At Early Withdrawal if a subject discontinues prematurely.
5. Administer the first dose of study drug within 9 hours (\pm 10 minutes) after the anesthetic block has been discontinued when a subject's pain intensity is ≥ 4 on the 11-point (0-10) NRS. Study drug will be administered from Time 0 through 48 hours within 10-minute windows.
6. Start stopwatches as soon as the first dose of study drug is administered. Stopwatches should be discontinued if the subject has not stopped them by the time of the second IP dose or first use of rescue medication (whichever occurs first).
7. Perform an oral cavity examination prior to and one hour after first dose.
8. Record concomitant medications.
9. Record AEs.
10. Subjects will complete a subject's global evaluation of study drug at the end of the treatment period (Day 3) before discharge from the study site or immediately before ET if a subject discontinues prematurely.
11. Dispense outpatient pain medication and an outpatient subject diary before discharge from the study on Day 3 (approximately 72 hours after completion of surgery).

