7.9.15 Time to meaningful relief

Time to meaningful relief is the time when the subject experiences relief that is meaningful after the administration of study drug and stops the second stopwatch, irrespective of the first stopwatch. If it is not stopped, time will be censored at the time of the second dose or the first use of rescue medication whichever comes first.

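### A subject who stops only the meaningful-relief stopwatch is right-censored for onset and for perceptible relief, although perceptible relief must have occurred by then

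*SAP*

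**What the plan says.** Under SAP 7.9.10 the subject stops the first watch on noticing any relief at all, and the second once the relief is one that he or she finds meaningful. Three endpoints are built on these two times.

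- **Onset of analgesia (SAP 7.9.11).** "Time to onset of analgesia is the time that the first stopwatch is stopped", on condition that the second is stopped too. Otherwise: "If both stopwatches are not stopped or just one stopwatch is stopped, then the time to analgesia will be censored" at the second dose or rescue, whichever is earlier.
- **First perceptible relief (SAP 7.9.14).** The event occurs when the subject "stops the first stopwatch (irrespective of the second stopwatch"). If the first watch is not stopped, "time will be censored at the time that the second stopwatch is stopped", or at the second dose or first rescue if one of those is earlier.
- **Meaningful relief (SAP 7.9.15).** The event occurs when the subject "stops the second stopwatch, irrespective of the first stopwatch".

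Protocol 7.3.2 ends the observation: "Stopwatches should be discontinued if the subject has not stopped them by the time of the second IP dose or first use of rescue medication". SAP 8.2.2.4, 8.2.2.8 and 8.2.2.9 analyse all three endpoints by Kaplan-Meier, with log-rank tests against placebo.

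**The concern.** Right-censoring says that the event had not happened by the censoring time. For a subject who stops only the second watch, the opposite is known: relief that is meaningful is also perceptible, so the first threshold was crossed at or before the second-watch time. Only the exact moment is missing. The SAP foresees the case in 7.9.14, since it names the second watch as a censoring trigger, but it gives the subject the wrong status.

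Time to onset is a secondary objective in Protocol 2.2 and SAP 2.1. Kaplan-Meier and log-rank methods assume that censoring carries no information about the event. Under 7.9.14 the relief itself triggers the censoring. Under 7.9.11 a subject with recorded meaningful relief stays in the risk set as if onset were still to come. Both rules lower the estimated proportion with relief and lengthen the estimated times.

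**Working it through.** **Step 1: one subject, three rules.** Let t2 be the second-watch time, with the first watch never stopped. The watches are discontinued at the second dose or first rescue, so t2 is no later than that point.

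| Endpoint | SAP status | What is known |
|---|---|---|
| Meaningful relief (7.9.15) | event at t2 | event at t2 |
| First perceptible relief (7.9.14) | event-free to t2, unknown afterwards | event in (0, t2] |
| Onset (7.9.11) | event-free to second dose or rescue | event in (0, t2], confirmed by meaningful relief |

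The last two rows conflict with what is known. No other section substitutes t2, uses interval censoring or plans a sensitivity analysis for this case.

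**Step 2: size, by illustration.** The plan has no figure to reproduce. The arm size of 15 is from SAP 4. The follow-up limit of 240 minutes is the 4-hour minimum dosing interval in Protocol 4.8. All relief times are assumed:

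- ten subjects get relief, with first-watch times 5, 8, 10, 12, 15, 18, 20, 25, 30 and 40 min and second-watch times 15, 20, 25, 30, 35, 40, 45, 60, 70 and 90 min;
- five get none and are censored at 240 min;
- the k subjects with the earliest relief stop only the second watch, and nobody stops only the first.

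Worked case, k = 1 (the subject with times 5 and 15 min):

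- *Onset.* The subject is carried to 240 min. Nine events remain: 9/15 = 60.0%, against 10/15 = 66.7%. The loss is 1/15 = 6.7 points.
- *Perceptible relief.* The subject is censored at 15 min. Four events (8, 10, 12, 15 min) give S = 11/15. Ten are then at risk and five have events, so S = 11/15 × 5/10 = 11/30. The proportion is 1 − 11/30 = 63.3%, a loss of 1/30 = 3.3 points.

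Kaplan-Meier proportion with the event by 240 min, and median in minutes (NR = not reached):

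| k | Meaningful | Perceptible, SAP | Onset, SAP | Both, with fix | Median perceptible, SAP | Median onset, SAP | Median, with fix |
|---|---|---|---|---|---|---|---|
| 0 | 66.7% | 66.7% | 66.7% | 66.7% | 25 | 25 | 25 |
| 1 | 66.7% | 63.3% | 60.0% | 66.7% | 30 | 30 | 25 |
| 2 | 66.7% | 59.1% | 53.3% | 66.7% | 30 | 40 | 25 |
| 3 | 66.7% | 54.1% | 46.7% | 66.7% | 40 | NR | 25 |
| 5 | 66.7% | 42.3% | 33.3% | 66.7% | NR | NR | 30 |

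From k = 1 onward, estimated meaningful relief exceeds estimated perceptible relief, which is impossible by definition. In real data this reversal of counts needs more subjects who stop only the second watch than subjects who stop only the first.

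**The case against.** **Onset is defined as perceptible relief confirmed by meaningful relief, so it needs a first-watch time.** This is the strongest point, and 7.9.11 follows that definition literally. But for this subject the confirmation is present. What is missing is the exact time, and t2 bounds it from above. An event at t2, or an interval ending there, respects that bound. Censoring at or after t2 contradicts it. The objection does hold for a subject who stops only the first watch: there the confirmation is absent, and censoring for onset is right.

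**Recording t2 as the onset time biases onset late.** True. It is the latest possible time, which is why interval censoring belongs beside it.

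**The pattern should be rare, and little rests on it.** This stands. Subjects are trained at screening and again before the block is discontinued, and staff start both watches. Stopping only the second watch departs from the instructions. Such subjects still count for meaningful relief, and Protocol 8.5.3.2 states that no formal inference is made on secondary endpoints. The estimates and log-rank p-values will still be reported.

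**Two stronger readings are tempting.** A reader might infer that the subject is treated as never having had perceptible relief. For onset that is close, although the status is still censored rather than failed. Under 7.9.14 the subject is event-free only to t2 and unknown afterwards. A reader might also infer that the rule penalises the faster-acting arm, because a rapid responder goes straight to meaningful relief. The documents do not support this: a subject who reaches both levels at once is told to stop both watches, and is then an event under both rules. Nothing shows that the pattern differs between arms.

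**Conclusion.** The point holds as a minor error in two censoring rules. By the SAP's own definitions, a subject who stops only the second watch has had perceptible relief by t2, yet 7.9.11 and 7.9.14 right-censor that subject while 7.9.15 counts an event.

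One such subject removes 1 of an arm's 15 possible onset events. That equals 6.7 percentage points in the illustration, where nobody is censored before the last onset; earlier rescue would change the weight. The loss for perceptible relief is smaller there, at 3.3 points. These sizes rest on assumed relief times, and the number of affected subjects is not given in the documents. SPID-48 and the sample size are untouched.

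**What to change.** Change one sentence in each of two SAP sections before unblinding:

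- **7.9.11:** if the second watch is stopped and the first is not, count onset as an event at the second-watch time. If the second watch is not stopped, censor at the second dose or first rescue, whichever is earlier.
- **7.9.14:** if only the second watch is stopped, count perceptible relief as an event at that time. If neither is stopped, censor at the second dose or first rescue, whichever is earlier.

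Add a sensitivity analysis that treats these times as interval-censored on (0, t2], and report the number of such subjects by arm so that the reader can judge the impact.

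The cost is two sentences and one short supplementary analysis, with no change to data collection. The downside is that the main analysis uses the latest possible time for these subjects, which makes their onset look slower than it was but keeps the event.
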